* For non-hysterectomized (NH) subjects, endometrial thickness will be measured after 3, 6, 9 and 12 months of treatment (Visits 4, 5, 6 and 7 of the Efficacy Study part and Visits 3, 4, 5 and 6 of the Safety Study part respectively) by transvaginal ultrasound (TVUS) and subjects will record daily the vaginal bleeding events. If at any time after the first 4 weeks of treatment a subject presents with persistent and/or recurrent bleeding, confirmed by the investigator or presents with a bi-layer endometrial thickness >10 mm as assessed by TVUS, an endometrial biopsy will be performed. If the biopsy shows disordered proliferative endometrium, hyperplasia or worse, the study drug will be discontinued, and the subject will be withdrawn from the study. The subject will be treated with P4 200 mg once daily for 14 days. If the endometrial event has not resolved, treatment with a progestin will be started according to local practice/guidelines. All NH subjects will receive treatment with 200 mg P4 for two weeks after completion of E4/placebo treatment.

Blinding:

Efficacy study part: double-blinded

Safety Study part: open-label

Trial Duration:

Individual subject participation in this trial may be up to 15 months. This includes a washout period of generally up to 8 weeks (usual washout period for most subjects), a screening period of generally up to 4 weeks, and a treatment period with E4 or placebo of up to 53 weeks. For non-hysterectomized subjects there will be an additional follow-up period of approximately 3 weeks.

For subjects requiring a longer washout (up to 6 months) participation period may be extended. For subjects who do not require a washout, the total participation period will be reduced by approximately 8 weeks.

The end of trial is defined as the date when the last patient has completed the last study visit.

Trial Population:

A total of ~1000 subjects will be enrolled in the study. Eligible subjects will be postmenopausal women, ≥ 40 up to ≤ 65 years of age, seeking treatment for relief of moderate to severe VMS associated with menopause.

Efficacy Study part: A total of ~600 subjects will be enrolled. Subjects (~300 hysterectomized and ~300 non-hysterectomized) need to have at least 7 moderate to severe bothersome VMS per day or at least 50 moderate to severe bothersome VMS a week in the last 7 consecutive days during the screening.

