Safety Study part: A total of ~400 subjects will be enrolled. Subjects (~200 hysterectomized and ~200 non-hysterectomized) should seek treatment for the relief of VMS (condition clinically indicated by the investigator) associated with menopause and have at least 1 moderate to severe menopausal related VMS per week.

Investigational Medicinal Product (dose, and mode of administration):

E4 15 mg (Arm 1) or E4 20 mg (Arm 2 and Arm 4), oral, once daily

Reference therapy (dose, and mode of administration):

Placebo, oral, once daily (Arm 3)

Other trial medication (dose, and mode of administration):

For non-hysterectomized subjects only:

- P4, 200 mg, oral, once daily for 14 consecutive days (after completion or discontinuation of E4/placebo treatment)
- Ad hoc treatment with a progestin according to local practice/guidelines if endometrial biopsy shows disordered proliferative endometrium, hyperplasia or worse

Conduct of the Trial:

For the Efficacy Study part at least 9 visits are planned: a Washout visit followed by a Screening period which will start with a Screening visit, a Baseline visit (Visit 1), and 6 On-treatment visits (Visits 2 to 7). The last treatment visit (Visit 7) is also the end of treatment (EoT) Visit, which will also occur in case of early discontinuation. For non-hysterectomized women an additional endometrial safety follow-up visit (Visit 8) is planned approximately 10 days after completion of the 14 days of P4 treatment, which will also occur in case of early discontinuation.

For the Safety Study part at least 8 visits are planned: a Washout visit followed by a Screening Period which will start a screening visit, a Baseline visit (Visit 1), and 5 On-treatment visits (Visits 2 to 6). The last treatment visit (Visit 6) is also the end of treatment (EoT) Visit, which will also occur in case of early discontinuation. For non-hysterectomized women an additional endometrial safety follow-up visit (Visit 7) is planned approximately 10 days after completion of the 14 days of P4 treatment, which will also occur in case of early discontinuation.

The screening period requires at least one visit, to occur as per protocol, at the beginning of the period, but some assessments (e.g., mammography, biopsy, transvaginal ultrasound [TVUS], electrocardiogram [ECG] and Papanicolaou [PAP] test) may require additional visits in case these assessments cannot be done during the same visit.

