2.1 Schedule of Trial Procedures Efficacy Study Part (*continued*)

CGI=Clinical Global Impression; discont=discontinuation; E2=estradiol; E4=estetrol; ECG=electrocardiogram; EoT=end of treatment; FSH= follicle stimulating hormone; gyn=gynecological; Hematol/chem=hematology/chemistry; I/E= in and exclusion criteria; med=medical; MENQOL=Menopause-specific Quality of Life; PAP= Papanicolaou; TSH= Thyroid stimulating hormone; TVUS=transvaginal ultrasound; VMS= vasomotor symptoms

- a) In case the subject uses medication that is not allowed during the duration of the trial, she is asked to stop this medication. The subject will return for the screening after a variable washout period that depends on the type of prior medication. Subjects not using medication that needs to be stopped and washed out can continue with the screening procedures.
Washout periods are: 1 week for vaginal hormonal products (rings, creams, gels); 4 weeks for transdermal estrogen or estrogen/progestin products; 8 weeks for oral estrogen and/or progestin and/or selective estrogen receptor modulator therapy; 8 weeks for intrauterine progestin therapy; 3 months for progestin implants or estrogen alone injectable drug therapy; 6 months for estrogen pellet therapy or progestin injectable drug therapy; 8 weeks for oral, topical, vaginal, patch of androgen/DHEA; 6 months for implantable or injectable androgen therapy; 2 weeks for phytoestrogens or black cohosh; 3 months for venlafaxine and desvenlafaxine if used for the treatment of VMS and 4 weeks all other non-hormonal prescription or over-the-counter treatments used for VMS.
- b) Every effort needs to be made to perform the procedures of the end of trial visit for those subjects that discontinue their participation.
- c) Visits will be scheduled in one of the seven days of week 5, week 9, week 13, week 29, week 41 and week 53, thus allowing a visit window of 7 days. Unscheduled visits may be needed during the treatment period for additional ultrasounds, biopsies or any other unforeseen safety assessments.
- d) Visit 8 for non-hysterectomized subjects only at approximately 10 days after completion of the progestin treatment.
- e) At washout visit and during the Screening Period only available I/E criteria at that time point will be checked.
- f) Blood pressure, heart rate, body height (during screening only) and body weight (during screening and EoT only).

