- l) TVUS at screening and EoT will be taken for all subjects who still have a uterus and/or ovaries. At all other time points a TVUS will be performed to monitor the endometrium thickness only for subjects who still have a uterus.
- m) Visit 7 for non-hysterectomized subjects only at approximately 10 days after completion of the progestin treatment.
- n) Non-hysterectomized subjects only.
- o) If the subject was treated for at least 12 weeks.
- p) Subjects are instructed during screening on how to fill in the diary and if needed can be re instructed.
- q) At each visit the diary will be checked. Completed pages will be collected and will remain at the study site.
- r) Progestin treatment for non-hysterectomized subjects only.
- s) If lipid and/or glucose parameters could be a reason of concern in the judgement of the Investigator, fasted blood sampling for lipid and glucose parameters assessment may be done during the Washout Visit. Otherwise, this assessment will be done during the Screening Period
- t) Laboratory tests may be repeated once during the screening period, at the discretion of the investigator. FSH measurement is not required for subjects with bilateral oophorectomy.
- u) In the event screening requirements cannot be met within 4 weeks, the screening period may be extended with prior Medical Monitor approval, but screening period may not exceed 8 weeks.

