7.1.2. Trial Duration

Individual subject participation in this trial may be up to 15 months. This includes a washout period of generally up to 8 weeks (usual washout period for most subjects), a screening period of up to 4 weeks, and a treatment period with E4 of up to 53 weeks. For non-hysterectomized subjects the trial duration will be 3 weeks longer due to an additional endometrium safety follow-up period of approximately 3 weeks.

For subjects requiring a longer washout (up to 6 months) participation period may be extended to allow this washout length. For subjects who do not require a washout, the participation period will be reduced by approximately 8 weeks.

The end of trial is defined as the date when the last patient has completed the last study visit.

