10. TRIAL ASSESSMENTS

10.1. Experimental Flow

For the Efficacy Study part at least 9 visits are planned: a Washout visit followed by a Screening period which will start with a Screening visit, a Baseline visit (Visit 1), and 6 On-treatment visits (Visits 2 to 7). The last treatment visit (Visit 7) is also the end of treatment (EoT) Visit, which will also occur in case of early discontinuation. For non-hysterectomized women an additional endometrial safety follow-up visit (Visit 8) is planned after completion of the 14 days of P4 treatment, which will also occur in case of early discontinuation.

For the Safety Study part at least 8 visits are planned: a Washout visit followed by a Screening period which will start with a Screening visit), a Baseline visit (Visit 1), and 5 On-treatment visits (Visits 2 to 6). The last treatment visit (Visit 6) is also the end of treatment (EoT) Visit, which will also occur in case of early discontinuation. For non-hysterectomized women an additional endometrial safety follow-up visit (Visit 7) is planned approximately 10 days after completion of the 14 days of P4 treatment, which will also occur in case of early discontinuation.

The screening period requires at least one visit, to occur as per protocol, at the beginning of the period, but some assessments (e.g., mammography, biopsy, TVUS, ECG, and PAP test) may require additional visits to another clinic in case these assessments cannot be done by the study site.

An overview of the trial visits and time windows for each visit is presented in Table 4

Table 4 Visit schedule and permitted time window

Study part	Visit number	Week number	Time window
Efficacy Study part	Washout visit	Week - 12 to week - 4 ¹	n.a.
	Screening period	Week - 4 to week - 1 ¹	n.a.
	Visit 1	Week 1	n.a.
	Visit 2	Week 5	Day 29 - 35
	Visit 3	Week 9	Day 57 - 63
	Visit 4	Week 13	Day 85 - 91
	Visit 5	Week 29	Day 197 - 203
	Visit 6	Week 41	Day 281 - 287
	Visit 7	Week 53	Day 365 - 371
Safety Study part	Visit 8 NH subjects only	Week 55/56	Day 379 - 392
	Washout visit	Week - 12 to week - 4 ¹	n.a.
	Screening period	Week - 4 to week - 1 ¹	n.a.
	Visit 1	Week 1	n.a.
	Visit 2	Week 5	Day 29 - 35
	Visit 3	Week 13	Day 85 - 91
	Visit 4	Week 29	Day 197 - 203
	Visit 5	Week 41	Day 281 - 287
	Visit 6	Week 53	Day 365 - 371
	Visit 7 NH subjects only	Week 55/56	Day 379 - 392

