10.1.5.7. Visit 7: End of Treatment/Early Termination Visit (week 53 or earlier)

Subjects will return to the trial site in week 53 for Visit 7. This will be the EoT and follow-up procedures will be performed. Subjects will take their last daily dose of the trial medication on the evening before or in the morning of the day of the EoT visit.

For subjects who terminate early, every reasonable effort should be made by the investigator to complete the final assessment procedures as specified in this section (see also Section 8.3). In case of early termination, treatment may have been stopped earlier.

The following observations/procedures are to be performed and checked at Visit 7:

- Physical examination
- Gynecological examination
- Breast examination
- Vital signs
- 12-lead ECG
- Endometrial biopsy if the subject has completed at least 12 weeks of treatment (for non-hysterectomized women only)
- TVUS (for women who still have uterus and/or ovaries)
- Digitalized mammography if the subject has completed at least 12 weeks of treatment and the last mammography was taken at least 9 months earlier
- MENQOL and CGI questionnaires
- Fasted blood sampling for:
 - Routine hematology, chemistry
 - Lipid metabolism
 - Glucose metabolism
 - Hemostasis parameters
 - Bone markers
 - Additional optional analysis
- Review of diary and collect completed pages (non-hysterectomized subjects)
- Dispense trial medication (P4 200 mg for non-hysterectomized subjects only)
- Review returned unused medication/drug accountability
- Record prior/concomitant medication
- Record AEs
- Complete end of trial form (hysterectomized subjects only)

For hysterectomized subjects: after completion of the Visit 7 procedures in the Efficacy Study part, the subject has completed the trial.

For non-hysterectomized subjects: after completion of Visit 7 procedures the subjects will start treatment with 200 mg P4 once daily for 14 days. Subjects should take the progestin medication as per investigator's instructions. Subjects are instructed to record the vaginal bleeding events and P4 intake in the diary. Subjects will return to the clinic approximately 10 days after completion of the progestin treatment for the endometrial safety follow-up visit.

10.1.5.8. Visit 8: Non-hysterectomized Subjects Only: Endometrial Safety Follow-up Visit (week 55/56 or earlier)

The following observations/procedures are to be performed and checked at Visit 8:

- TVUS
- Return of diary
- Review of diary

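### Protocol Table 4 opens the post-progesterone follow-up window at Day 379, which is 9 to 10 days before the earliest date the protocol text implies and usually still a progesterone dosing day.

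*Protocol*

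**What the plan says.** Table 4 in Protocol Section 10.1 places EoT (Efficacy Visit 7, Safety Visit 6) in Week 53, Day 365-371. It places the follow-up visit for non-hysterectomized women at "Week 55/56 Day 379 - 392" in both study parts. Both windows count from Day 1 of treatment.

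The text counts from the end of P4 instead:

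- The Synopsis (Conduct of the Trial) has the visit "planned approximately 10 days after completion of the 14 days of P4 treatment, which will also occur in case of early discontinuation".
- Section 2.1, footnote d: "Visit 8 for non-hysterectomized subjects only at approximately 10 days after completion of the progestin treatment".
- Section 2.2, footnote m: "Visit 7 for non-hysterectomized subjects only at approximately 10 days after completion of the progestin treatment".
- Section 10.1.5.7, after stating that 14 days of P4 begin once the EoT procedures are done: "Subjects will return to the clinic approximately 10 days after completion of the progestin treatment for the endometrial safety follow-up visit". Section 10.1.6.6 says the same for the Safety Study part.

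Two passages give the total length. The Synopsis says "For non-hysterectomized subjects there will be an additional follow-up period of approximately 3 weeks", and Section 7.1.2 refers to an "additional endometrium safety follow-up period of approximately 3 weeks".

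One sentence is looser. For the Efficacy Study part, the visit overviews in Sections 7.1.1 and 10.1 say only that "an additional endometrial safety follow-up visit (Visit 8) is planned after completion of the 14 days of P4 treatment", with no interval. The matching Safety Study part sentences give about 10 days.

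**The concern.** A permitted window should contain the days on which the visit meets its purpose and exclude those on which it cannot. This visit measures endometrial thickness by transvaginal ultrasound (TVUS) after P4 has been completed. For women not withdrawn for disordered proliferative endometrium or worse, it is the only scheduled scan after P4. A window that opens while most women are still taking P4 works against that purpose.

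A site that books from Table 4 could scan during P4, or a day or two after it, and record the visit as in window. Another site following the text would scan about 10 days after the last dose. The two scans would carry the same visit label. The Safety Study part SAP would not separate them: Section 7.1 analyses by visit whatever the window deviation, and Appendix 1, Table 7, which covers imaging, sets no day limits.

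**Working it through.** **Inputs.** EoT on Day 365-371 and follow-up on Day 379-392 (Table 4); P4 for 14 days starting after the EoT procedures (Sections 10.1.5.7 and 10.1.6.6); follow-up about 10 days after P4 ends (Synopsis; Section 2.1 footnote d; Section 2.2 footnote m). The documents do not say whether the first P4 dose falls on the EoT day or the next day, so both are shown.

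**Reproducing the plan's figure.** Week w runs from Day 7(w - 1) + 1 to Day 7w. Week 53 is Day 365-371. Weeks 55 and 56 together are Day 379-392. Table 4 is therefore the correct calendar span of its week label; the question is whether that label fits the text.

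**Target day.** Last P4 day = first P4 day + 13. Target = last P4 day + 10. The number of window days on P4 is last P4 day - 379 + 1, or 0 if that is negative.

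| EoT day | Same-day start: last P4 day | Target | Window days on P4 | Next-day start: last P4 day | Target | Window days on P4 |
|---|---|---|---|---|---|---|
| 365 | 378 | 388 | 0 | 379 | 389 | 1 |
| 366 | 379 | 389 | 1 | 380 | 390 | 2 |
| 367 | 380 | 390 | 2 | 381 | 391 | 3 |
| 368 | 381 | 391 | 3 | 382 | 392 | 4 |
| 369 | 382 | 392 | 4 | 383 | 393 | 5 |
| 370 | 383 | 393 | 5 | 384 | 394 | 6 |
| 371 | 384 | 394 | 6 | 385 | 395 | 7 |

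**Lower end.** The earliest target is Day 388 or 389. The window opens 388 - 379 = 9 or 389 - 379 = 10 days before it. Day 379 is a dosing day for 6 of the 7 EoT days with a same-day start and for all 7 with a next-day start.

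**Against the three-week follow-up.** EoT + 21 gives Day 386 (365 + 21) to Day 392 (371 + 21). Day 379 is only 8 (379 - 371) to 14 (379 - 365) days after EoT.

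**Upper end.** Day 392 falls 2 to 3 days before the latest target (394 or 395) and equals 371 + 21. That is within the latitude of an approximate interval, so it is not disputed.

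**The case against.** The strongest reply is that the correct interval is hard to miss. It appears in the Synopsis, in footnotes attached to the Week 55/56 columns, in the design section, in both EoT visit instructions and, for the Safety Study part, just above Table 4. A scan on a P4 day would fail those instructions and so be a deviation under Section 11.2, whatever Table 4 says. The two rules can also be met together: for every allowed EoT day, Day 392 lies at least 7 days after the last dose (392 - 385 = 7 in the worst case).

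This stands as a limit on impact. A reader might infer that the protocol intends or sanctions scanning during P4. It does not: the text requires P4 to be complete. But the reply leaves the conflict in place. An approximate 10-day interval can absorb two or three days, not a visit made before the course has ended. The same scan would be in window by the table and a deviation by the text.

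It is also fair that little formal analysis rests on this scan. SAP Section 7.7.1.11 names Visits 3 to 6 for on-treatment thickness and does not name the follow-up visit. The endometrial safety endpoint uses the consensus biopsy diagnosis (SAP Section 7.7.1.12.1). Women with disordered proliferative endometrium or worse have their own rule of about 10-14 days after progestin (Protocol Section 10.4.10).

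**Conclusion.** The inconsistency is real and minor. At its lower end, Table 4 contradicts the protocol's own timing by 9 to 10 days, and its first day is a dosing day for 6 or 7 of the 7 EoT days. The conclusion assumes EoT within its own window, a full 14-day course, and P4 started on the EoT day or the day after; the choice between those two shifts the result by one day. The consequences are confined to scheduling, deviation classification and the consistency of the post-P4 thickness scan. No primary endpoint, sample size, error rate or exclusion rule is affected.

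Three stronger readings are not supported:

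- A reader might turn the table of permitted days into a share of visits expected to be mistimed. The documents give no distribution of visit dates and no minimum acceptable gap after P4, so any such percentage would rest on an arbitrary cut-off and predict nothing.
- A reader might think SAP Table 5, which repeats Day 379-392, carries the error into the thickness results. That table governs efficacy visits. Imaging falls under Table 7, so changing Table 5 would alter no TVUS result.
- A reader might infer that early discontinuers have no timing rule. They do: the Synopsis applies the 10-day interval to them, and the visit headings in Sections 10.1.5.8 and 10.1.6.7 allow for an earlier week. They lack only a matching window in Table 4.

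**What to change.** In Table 4 and the Week 55/56 columns of Sections 2.1 and 2.2, replace the study-day window with one counted from the last P4 intake: 10 days, with a stated tolerance that excludes dosing days. With -3/+4 days as an example, the visit falls 7 to 14 days after the last dose. For completers that is Day 385-398 with a same-day start (378 + 7 to 384 + 14) or Day 386-399 with a next-day start (379 + 7 to 385 + 14), roughly Weeks 56 and 57. Apply the same rule to early discontinuers. Put the approximate 10-day interval into the Efficacy Study part sentences of Sections 7.1.1 and 10.1.

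Optionally, flag follow-up scans taken on P4 or well before the interval. P4 intake is already in the diary (Section 10.1.7) and scan dates are collected, so this needs one derived variable. If most follow-up visits are already done, the flag is the useful part.

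The cost is one protocol clarification, with no new visit, procedure or data item. The downside is that some visits move a few days later, under the example tolerance by no more than 399 - 392 = 7 days past the present close of the window.

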10.1.1. Informed Consent Procedure

When a suitable candidate is identified by the Investigator among the outpatients coming to the trial site, the investigator or designated healthcare professional will ask the subject about her willingness to be included in the clinical trial. The subject is to be informed verbally and in writing about the nature, risks, benefits, and expectations of participating in the clinical trial and a copy of the subject informed consent form (ICF) is to be given to the subject in the appropriate language. Following this, subjects will be allowed sufficient time, in their own opinion, to consider trial entry, and will be offered the opportunity to ask any further questions prior to completing the ICF. The subject ICF is to be signed by the subject and countersigned by the attending investigator or designee prior to proceeding with the Washout/Screening visit and a copy of the signed ICF is provided to the subject.

10.1.2. Washout Visit

All subjects will be pre-screened at the Washout visit and Informed Consent (IC) is taken at this visit. After signing the ICF the following procedures will be performed:

- Check of already available inclusion/exclusion criteria
- Review of the drug treatments/therapy
- If lipid and/or glucose parameters could be a reason of concern in the judgement of the investigator, fasted blood sampling for lipid and glucose parameters assessment may be done during this visit. Otherwise, this assessment will be done during the Screening Period.
- Medical and gynecological history
- Obtain demographic data

In case the subject uses medication for which a washout is necessary (see Section 9.6.1) the screening procedures will be halted. The subject is asked to stop taking this medication and will return for screening after the required washout period (see Section 9.6.1).

In case no washout period is required the subject will immediately continue the procedures of the Screening Visit. For these subjects the Washout visit and Screening visit may occur at the same time.

